One goal of the proposed clinical investigation is to test the null hypothesis that the population mean is 82.16 points. The criterion for significance (alpha) has been set at 0.05. The test is 2-tailed, which means						

that effects in both directions will be interpreted. With the proposed sample size of 10 cases, the clinical investigation will have power of 80.3% to yield a statistically significant result. This computation assumes that the population from which the sample will be drawn has a mean of 82.16 points with a standard deviation of 16.76 points. The observed value will be tested against a theoretical value (constant, non-inferiority margin) of 65.40 points.

IBM SPSS Sample Power Output – Screenshot

Estimated overall drop-out rate is 56% which leads to the requirement of enrolling additional 6 subjects into the clinical investigation.

Sample Size	Number of subjects to be enrolled: 16 subjects (rounded up to 20 subjects)
Overall Sample Size (multiplied by number of indications (=5))	100 subjects

Table 2: Sample Size Justification

In conclusion, the calculated number of subjects to be enrolled (10) plus the estimated overall drop-out rate of 56% predicts enrollment of 20 subjects per cleared indication (five) to reflect the underlying subject population adequately. As a result, an enrollment target of 100 subjects in total will be aspired.

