11.3.2. Primary Analysis / Endpoint

The objective of the clinical investigation is to demonstrate non-inferiority (equal or better) of the ASES Shoulder Score in relationship to the officially cleared indications in comparison to respective clinical outcome data in the scientific literature.

[figure not shown]
Data collection of ASES Shoulder Score will start pre-operatively and will be collected according to schedule in Table 1. This will be repeated annually in all subjects who have the total or partial prosthesis with full or partial implant survival (including all subjects without removal of all endo-prosthesis components).

The 24 months post-operative results for subjects implanted with ReUnion TSA System will be compared to a historical group and results reported by respective clinical outcome data in the scientific literature. The benchmark sources and values will serve as the control group for the ReUnion TSA System subjects.

Higher ASES Shoulder Score results are linked to better subject results and vice versa.

The clinical investigation endpoint is non-inferiority to the control, meaning the clinical investigation result should be equal or better than the control. In this clinical investigation, an equal or better ASES Shoulder Score result means equal or more (\geq). As only results from samples will be captured, results are mostly estimates of the true population parameter. These estimates vary by a certain area, where it is expected that the true population parameter falls within. Based on this, it is required to specify a lower limit for the acceptable difference or zone of indifference, denoted as $-\theta$.

Hypotheses are developed to allow for a comparison of the 24 months post-operative ASES Shoulder Score effectiveness / performance between the two underlying populations. The 24 months post-operative ASES Shoulder Score is the primary endpoint of this clinical investigation. Hypothesis tests will be one-sided with a significance level α of 5%.

Hypothesis	Equations	Interpretation
Null (H_0)	$A - B < -\theta$	Central tendency of A is inferior to the central tendency of B.
	ReUnion TSA System – Control (Benchmark) $< -\theta$	
Alternative (H_1)	$A - B \geq -\theta$	Central tendency of A is non-inferior to the central tendency of B.
	ReUnion TSA System – Control (Benchmark) $\geq -\theta$	
		
Possible Evidence (p)	Possible Decisions	Possible Conclusions – ASES score

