3.2. SAMPLE SIZE

The determination of sample size is based on benchmark sources and values. To account for an estimated appropriate overall drop-out rate, Stryker intends to enroll the calculated number of subjects, multiplied

[figure not shown]
by the number of cleared indications to reflect the underlying subject population adequately. For details, please see Table 3.2.

Benchmark and Objectives for Clinical Investigation					
Endpoint		Non-inferiority (equal or better) of the ASES Shoulder Score in relationship to the officially cleared indications in comparison to respective clinical outcome data in the scientific literature.			
Estimated drop-out rate		56% (confirmed by Medical Expert, see Cuff et al.) Cuff et al. Reverse Shoulder Arthroplasty for the Treatment of Rotator Cuff Deficiency: A Concise Follow-up, at a Minimum of 10 Years, of Previous Reports. J Bone Joint Surg Am. 2017 Nov 15;99(22):1895-1899. doi: 10.2106/JBJS.17.00175.			
Benchmark Sources & Values ASES [points]					
Source		n	Mean	Std. Dev.	Comments No.
No.	Title				
1	Irlenbusch et al. [10]	73	77.9	N/A	Conflict related to Follow-Up times in abstract vs method vs result section.
2	Flurin et al. [20]	73	90.3	14.6	Not clear if SD or 95% CI
3	Press et al. [22]	34	82.6	19.4	
4	Hsu et al. [23]	25	94.4	N/A	
5	Kiet et al. [26]	40	80	21	N changed from 45 to 40
6	Steen et al. [29]	96	80.4	22.4	Not clear if SD or 95% CI
7	Gulotta et al. [34]	40	80.1	10.1	
8	Petri et al. [49]	43	83.5	13.1	
9	Schoch et al. [62]	78	88.4	16.7	
10	Alentorn-Geli et al. [70]	38	64	N/A	TSA und HA combined.
Identified Cleared Indications					
No.	Indication				
1	Post-traumatic arthritis				
2	Degenerative arthritis				
3	Rheumatoid arthritis				
4	Revision of previously failed shoulder joint replacement				
5	Aseptic necrosis				
Explorative Meta-Analysis - ASES (single group)					
Acceptance Criteria					
Confidence Interval (CI)					0.95 (95%) two-sided
Software Used					IBM SPSS V20
Case Processing Summary					
		Cases			
		Valid		Missing	
		N	Percent	N	Percent
Mean ASES ReUnion_TSA_CER		10	100,0%	0	0,0%
Std.Dev. ASES ReUnion_TSA_CER		7	70,0%	3	30,0%
				10	100,0%

Descriptives								
			Statistic					
Std.Dev. ASES ReUnion_TSA_CER	Mean	16,7571						
	95% Confidence Interval for Mean	Lower Bound	12,6353					
		Upper Bound	20,8790					
	Median	16,7000						
	Std. Deviation	4,45678						
	Minimum	10,10						
	Maximum	22,40						
	Interquartile Range	7,90						
Mean ASES ReUnion_TSA_CER	Mean	82,1600						

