	95% Confidence Interval for Mean	Lower Bound	76,2372					
		Upper Bound	88,0828					
	Median	81,5000						
	Std. Deviation	8,27945						
	Minimum	64,00						
	Maximum	94,40						
	Interquartile Range	9,40						
								
Red line: Pooled mean ASES Blue lines: 95% CI of pooled mean ASES Black line: Pooled median pooled ASES Box: Interquartile Range Green Line: Pooled mean ASES minus pooled std. dev. ASES (16.76) $82.16 - 16.76 = \mathbf{65.40 \text{ points}}$								
Acceptance Criteria for Sample Size Calculation								
Significance Level (α)	0.05 (5%)							
Power (1- β)	0.80 (80%)							
Confidence Interval (CI)	0.95 (95%)							
Tails	2							
Path	Non-inferiority – ReUnion TSA (A) \geq Benchmark (B, explorative meta-analysis in this document)							
Hypotheses Pair	Null (H_0)	$A - B < -\theta$						
	Alternative (H_1)	$A - B \geq -\theta$						
Benchmark Timepoint	24 months postoperative							
Benchmark n (sources)	10							
Benchmark Mean	82.16 (pooled mean ASES [points])							
Benchmark Std. Dev.	16.76 (pooled std. dev. ASES [points])							
Benchmark Value Non-Inferiority Margin (- θ)	Pooled mean ASES minus pooled std. dev. ASES (16.76) $82.16 - 16.76 = \mathbf{65.40 \text{ points}}$							
Software Used	IBM SPSS Sample Power V3.0							
IBM SPSS Sample Power Output								
One goal of the proposed clinical investigation is to test the null hypothesis that the population mean is 82.16 points. The criterion for significance (alpha) has been set at 0.05. The test is 2-tailed, which means that effects in both directions will be interpreted. With the proposed sample size of 10 cases, the clinical investigation will have power of 80.3% to yield a statistically significant result. This computation assumes								

that the population from which the sample will be drawn has a mean of 82.16 points with a standard deviation of 16.76 points. The observed value will be tested against a theoretical value (constant, non-inferiority margin) of 65.40 points.

IBM SPSS Sample Power Output – Screenshot

Estimated overall drop-out rate is 56% which leads to the requirement of enrolling additional 6 subjects into the clinical investigation.

Sample Size	Number of subjects to be enrolled: 16 subjects (rounded up to 20 subjects)
Overall Sample Size (multiplied by number of indications (=5)	100 subjects

Table 3.2: Sample Size Justification

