In conclusion, the calculated number of subjects to be enrolled (10), plus the estimated overall drop-out rate of 56%, leads Stryker's enroll 20 subjects per cleared indication (5) to reflect the underlying subject population adequately. As a result, an enrollment target of 100 subjects in total will be aspired (ideally, but not necessarily, composed with 20 subjects per indication).

4. Methods

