6.6. ANALYSIS OF CI ENDPOINTS

Evaluation Variable / Question	Level of Measurement	Analysis Plan					
Endpoints – Primary Endpoint							

Use variable Total ASES Shoulder Score 24 Months [points]: Based on the underlying distribution of the data and the result of the normality assessment, either the parametric one-sample t-test or the non-parametric one-sample sign test will be used to compare the 24 months postoperative ASES Shoulder Score results of the ReUnion TSA group against the lower maximum acceptable difference ($-\theta$) of 65.40 points.
 
The analysis of the primary endpoint will be part of the final report.
							

Table 6.6.1: Endpoints – Primary Endpoint Tables List

Evaluation Variable / Question	Level of Measurement	Recode and Analysis Plan	Inclusion		
Adverse Events – Time to (earliest) Device-Related Adverse Event / Incident			IR	FR	N/A
Creation of variable Difference between Date of Surgery [dd.mm.yyyy] and Date of First Device Related Adverse Event [dd.mm.yyyy] in days / (Variable(s): VISITDT; AEONSTDT)	Quantitative, ratio	Case summary with number and percentage of valid cases/values, missing cases/values (if any) and total cases/values. Mean, median, interquartile range, maximum, minimum, standard deviation, 95% confidence interval for mean, Shapiro-Wilk Test.		X	
Creation of variable Difference between Date of Surgery [dd.mm.yyyy] and Date of “most recent” Visit [dd.mm.yyyy] in days / (Variable(s): VISITDT)	Quantitative, ratio	N/A (Analyzed above), used for survivorship		X	

Create new variable “Grouping variable – First Device Related Adverse Event” (Variable(s): AEONSTDT)	Qualitative, nominal	- censored = survivors - events = first (earliest) Device Related Adverse Event		X	
Create new variable “Combined Time – First Device Related Adverse Event” (Variable(s): AEONSTDT)	Quantitative, ratio	- Use time between surgery and “most recent” visit for surviving subjects - Use time between surgery and first device related adverse event for subjects with device related adverse event		X	

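### The 56% drop-out allowance is computed as n × (1 + d) = 16 instead of n/(1 − d) = 23, and the printed 80.3% power is for a two-tailed test of 10 cases, not the planned one-sided whole-group test

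*Protocol*

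**What the plan says.** Protocol section 11.1 (Table 2) and SAP section 3.2 (Table 3.2) carry the same calculation.

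- **Power.** "With the proposed sample size of 10 cases, the clinical investigation will have power of 80.3% to yield a statistically significant result". The inputs are a true mean of 82.16, an SD of 16.76, a comparison value of 65.40, alpha 0.05 and two tails. Protocol section 11 repeats the 10 cases and the 80.3%.
- **Drop-out.** "Estimated overall drop-out rate is 56% which leads to the requirement of enrolling additional 6 subjects into the clinical investigation". The result line in the SAP begins "Number of subjects to be enrolled: 16 subjects (rounded up to 20 subjects". The 20 is then multiplied by five cleared indications to give 100.
- **Source of the 56%.** A report entitled "Reverse Shoulder Arthroplasty for the Treatment of Rotator Cuff Deficiency: A Concise Follow-up, at a Minimum of 10 Years".
- **SD.** Both tables call 16.76 a pooled standard deviation. Two of the seven contributing values carry the comment "Not clear if SD or 95% CI".

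The analysis sections describe a different test. Protocol 11.3.2 and SAP 3.1.1 say "Hypothesis tests will be one-sided with a significance level" of 5%. SAP 6.6 plans one comparison of the 24-month "ASES Shoulder Score results of the ReUnion TSA group against the lower maximum acceptable difference" of 65.40 points, by one-sample t-test or sign test depending on normality. No test by indication is planned. SAP 3.2 adds that the 100 would be "ideally, but not necessarily, composed with 20 subjects per indication".

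**The concern.** Two steps in the sample-size argument looked wrong.

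First, adding 56% of 10 to 10 does not protect against losing 56% of those enrolled, because the loss applies to the enrolled number and not to the target. The result should be larger than 16, and possibly larger than the rounded 20.

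Second, the only power figure in either document is for 10 cases and two tails. The primary analysis is one-sided and uses the whole device group.

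This calculation is the only justification given for enrolling 100 people. A reader could take it to mean that each indication has 80% power after drop-out, and could not find the number of evaluable subjects, or the power, for the test that decides the primary endpoint.

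**Working it through.** **Inputs** (Table 2 and Table 3.2): mean 82.16, limit 65.40, SD 16.76, alpha 0.05, n = 10, drop-out d = 0.56. The standardised difference is (82.16 − 65.40)/16.76 = 1.0.

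**1. Reproduce the printed power.** For a one-sample t-test, power comes from the noncentral t with n − 1 degrees of freedom and noncentrality 1.0 × √n. At n = 10:

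- two-sided 5%: 0.803, matching the printed 80.3%
- one-sided 5%: 0.898
- normal approximation: 0.885 two-sided, 0.935 one-sided

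Of these, only the two-sided t-test gives the plan's figure.

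**2. Reproduce the printed enrolment.** 10 × (1 + 0.56) = 15.6, so 16. This matches the extra 6 subjects.

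**3. Correct inflation.** 10/(1 − 0.56) = 10/0.44 = 22.7, so 23.

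- 16 × 0.44 = 7.0 evaluable
- 20 × 0.44 = 8.8 evaluable
- 16 keep 10 only if loss is at most 1 − 10/16 = 37.5%
- 20 keep 10 only if loss is at most 1 − 10/20 = 50%

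**4. Power at the numbers that would remain.** Sign-test figures are exact and one-sided. They assume normal scores, so that P(score > 65.40) = Φ(1) = 0.841.

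| Evaluable | t, two-sided | t, one-sided | Sign test (critical count) |
|---|---|---|---|
| 7 | 0.600 | 0.754 | not computed |
| 8 | 0.681 | 0.815 | 0.63 (7) |
| 9 | 0.748 | 0.862 | 0.57 (8) |
| 10 | 0.803 | 0.898 | 0.51 (9) |
| 44 | > 0.999 | > 0.999 | 0.9998 (28) |

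At the expected 8.8, the t-test formula gives about 0.74 two-sided and 0.85 one-sided. Sign-test power falls from 8 to 10 because the attainable significance level drops in steps (0.035, 0.020, 0.011). Under the planned one-sided t-test, 8 evaluable already give 80% power. That needs 8/0.44 = 18.2, so 19 enrolled, which 20 covers.

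**5. The test that will be run.** 100 × 0.44 = 44 evaluable, with power above 0.999 by either test.

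**6. Drop-out at 24 months.** The documents give no 24-month rate, so a range is assumed:

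| Assumed drop-out | Left of 100 | Left of 20 |
|---|---|---|
| 10% | 90 | 18 |
| 30% | 70 | 14 |
| 50% | 50 | 10 |
| 56% | 44 | 8.8 |

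**7. The SD.** The seven reported SDs sum to 117.3, and 117.3/7 = 16.757, so 16.76 is a simple mean. The pooled value, √[Σ(n − 1)SD² / Σ(n − 1)], is 17.77 over all seven sources and 16.46 without the two of doubtful meaning. With SD 17.77 and the limit kept at 65.40, the standardised difference is 16.76/17.77 = 0.943. Power at 44 evaluable stays above 0.999.

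**The case against.** The strongest reply is that nothing in the trial depends on this. One hundred subjects are ample for the single primary test, and two-tailed planning is conservative because it asks for 10 where the one-sided test needs 8. That is correct, and it limits the point to the written justification.

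Protocol section 11 and SAP 3.2 also contain a sentence that ties the multiplication by five to drop-out. Read that way, 44 remain where 10 are needed. But both tables apply the 56% explicitly first, reach 16, round to 20, and only then multiply by the number of indications. The sentence does not repair that step.

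Next, 56% is called an overall rate and the study runs to 10 years, so it may never have been meant for 24 months. At a loss of 50% or less, 20 do keep 10. This is fair, and it is why a separate 24-month range is needed. The plan nevertheless applies 56% to a power calculation for the 24-month endpoint, and at that rate 16 and 20 both fall short of 10.

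Finally, the documents never say in so many words that the primary test combines the indications, and the stated objective refers to the cleared indications. The analysis sections nevertheless describe one comparison of the whole group, and SAP 6.6 lists no other. If power by indication was intended, the plan should say so.

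Two cautions on presentation are also fair: sign-test power should carry its normality assumption, and power at a fractional 8.8 subjects is only indicative.

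**Conclusion.** The concern holds and should be fixed. The drop-out step gives 16 where the plan's own inputs require 23, and rounding to 20 does not close the gap to 10 evaluable at 56% loss. The printed 80.3% belongs to a two-tailed test of 10 cases; the planned one-sided test has 89.8% at that number and is in any case run on the whole group.

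The primary test is not underpowered. With 44 evaluable of 100, power exceeds 99.9%. This rests on a true mean of 82.16, an SD of 16.76 (or 17.77), a limit of 65.40 and, for the sign test, normal scores. The shortfall matters only if each indication was meant to keep 10 evaluable subjects, which the documents do not establish.

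**What to change.** Keep the 100 subjects, the test and the limit. In protocol sections 11 and 11.1 and SAP 3.2, replace the step from 10 to 16 and the 80.3% text with wording such as:

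> One-sample t-test against 65.40, one-sided 5%, difference 16.76, SD 16.76 (unweighted mean of seven reported SDs): 10 evaluable subjects give 89.8% power. At 56% drop-out, 10 evaluable need 10/(1 − 0.56) = 23 enrolled. The primary test is run once, over all indications combined. One hundred enrolled leave about 44 evaluable at 56% drop-out, with power above 99.9% (t-test, or sign test if scores are normal). Twenty enrolled in one indication would leave about 8 or 9 evaluable (t-test power 0.82 to 0.86 one-sided, 0.68 to 0.75 two-sided; one-sided sign test about 0.57 to 0.63 under normality). No power is claimed by indication, and any such result is descriptive.

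The 23 only shows the correct inflation; it is not a request for 23 × 5 = 115 subjects.

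In addition:

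- use the same sidedness in the sample-size tables and the analysis sections;
- state that the 56% comes from follow-up of at least 10 years, and show the evaluable numbers over a range of 24-month drop-out, as in the table above.

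The cost is text only: no extra subjects and no change to the analysis. The printed 80.3% and the 16/20 argument are withdrawn.

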11.2. ANALYSIS POPULATIONS

It is expected that during this clinical investigation only one population for ReUnion TSA System will exist and all subjects will be analyzed “Per Protocol” (PP). However, it cannot be fully avoided that in theory subjects might need to be excluded from the PP population. In this occasion, there will be two groups being fully analyzed to ensure transparency and avoid bias.

The groups are defined as follows:

- Intent-to Treat Population**

The Intent-to-Treat (ITT) Population is defined to be all enrolled subjects. An enrolled subject is a subject that has signed informed consent, all screening procedures have been successfully completed, is eligible and can receive treatment. The ITT population will not be analyzed for the annual reports and will only be included in the final report.

- Per Protocol Population**

The PP Population is defined to be all subjects in the ITT Population with no major CIP violations. The CIP violations that will exclude a subject are as follows:

- The subject does not receive the ReUnion TSA System
- The subject does not meet all eligibility criteria
- The subject has a protocol deviation that is considered likely to affect subject outcomes

After the clinical investigation has been completed, a review of the data will be conducted to determine which subjects are to be excluded from the PP population.

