This investigation is a prospective, multicenter clinical investigation. It is anticipated that a total of one hundred (100) subjects will be enrolled at approximately 4-7 sites. Neither subjects nor investigators are blinded to treatment and the clinical investigation does not include a contemporaneous control. The clinical investigation has been designed to follow the surgeon's standard of care for joint arthroplasty subjects, which entails clinical evaluation on a regular ongoing basis, or as needed should the subject become symptomatic in the treated joint. The enrollment period is expected to occur over 14 months.

8. Objective

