5.1. ANALYSIS POPULATION

It is expected that during this clinical investigation only one population for ReUnion TSA System will exist and all subjects will be analyzed “Per Protocol” (PP). However, it cannot be fully avoided that in theory subjects might need to be excluded from the PP population. In this occasion, there will be two groups being fully analyzed to ensure transparency and avoid bias.

The groups are defined as follows:

- **Intent-to Treat Population**

The Intent-to-Treat (ITT) Population is defined to be all enrolled subjects. An enrolled subject is a subject that has signed informed consent, all screening procedures have been successfully completed, is eligible and can receive treatment. The ITT population will not be analyzed for the annual reports and will only be included in the final report.

- **Per Protocol Population**

The PP Population is defined to be all subjects in the ITT Population with no major CIP violations. The CIP violations that will exclude a subject are as follows:

- The subject does not receive the ReUnion TSA System
- The subject does not meet all eligibility criteria
- The subject has a clinical investigation plan violation that is considered likely to affect subject outcomes.

After the clinical investigation has been completed, a review of the data will be conducted to determine which subjects are to be excluded from the PP population.

The following tables will be created for interim/annual and final reports related to the clinical investigation populations and progress:

Evaluation Variable / Question	Level of Measurement	Analysis Plan
All Forms – Overview & Progress Report		
Counting of available subjects Subject Population by Site (Variable(s): SITENUM; SUBID)	Qualitative, nominal	Proportions, frequencies, column and row totals, missing proportion (if any).
Counting of available subjects Subject Population by Visit (Variable(s): SITENUM; SUBID; VISITDT)	Qualitative, nominal	Proportions, frequencies, column and row totals, missing proportion (if any).
Counting of available subjects Subject Population by Visit and by Site (Variable(s): SITENUM; SUBID; VISITDT)	Qualitative, nominal	Proportions, frequencies, column and row totals, missing proportion (if any).

Table 5.1: Populations and Progress Tables List

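### Per-protocol exclusions rest on an open, outcome-worded criterion judged when scores are known, and no population is named as deciding the primary test

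*Protocol*

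**What the plan says.** Protocol 11.2 gives three grounds for leaving the PP population: not receiving the device, not meeting all eligibility criteria, and the open one, "The subject has a protocol deviation that is considered likely to affect subject outcomes". SAP 5.1 has the same three, the last reading "The subject has a clinical investigation plan violation that is considered likely to affect subject outcomes". Neither document lists such deviations, defines a major violation, names who decides, or withholds ASES scores from that person. Protocol section 12 and SAP 5.4 require only that deviations be recorded, reported and listed.

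On timing, Protocol 11.2 says: "After the clinical investigation has been completed, a review of the data will be conducted to determine which subjects are to be excluded". SAP 5.1 agrees.

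Both sections expect that nobody will be excluded, so that a single PP population exists. If someone is, "there will be two groups being fully analyzed to ensure transparency and avoid bias". The second group is ITT, which is kept out of the annual reports and appears only in the final report.

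The primary test compares the 24-month ASES score with the fixed value 65.40, one-sided at 5%, by one-sample t-test or sign test according to a normality assessment (Protocol 11.3.2, SAP 3.1.1). Protocol 11.5.1 and SAP 4.2 place it in the annual report once all subjects have completed 24 months. SAP 6.6 places it in the final report. On design, Protocol section 7 states: "Neither subjects nor investigators are blinded to treatment and the clinical investigation does not include a contemporaneous control".

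**The concern.** The criterion is worded by presumed effect on the outcome and applied when the outcome can be seen. The same deviation is more easily judged influential in a subject with a poor score than in one with a good score. Nothing in either document guards against this, because the set of qualifying deviations is open and the scores are not withheld. Bringing the review forward to month 24 would not by itself cure it.

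A single-arm test is exposed. There is no second arm in which similar selection could offset it, and dropping low scores raises the mean and shrinks the standard deviation together. As an illustration, suppose three of 44 subjects lie on average 2 SD (33.52 points) below the overall mean. Removing them raises the mean by 3 × 33.52 / 41 = 2.45 points. The standard error is about 16.76 / √41 = 2.62 points, so the shift is roughly 0.9 of a standard error before any fall in the SD.

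At stake is the 5% error rate of the non-inferiority claim, and whether it is clear which result carries that claim if PP and ITT differ.

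**Working it through.** **Inputs.** Limit 65.40, planning mean 82.16, SD 16.76, n = 10 and power 80.3% (Protocol Table 2, SAP Table 3.2). One-sided α of 5% (Protocol 11.3.2). Enrolment 100 and overall drop-out 56% (Protocol 11.1). Evaluable n at 24 months is not given, so the range is bracketed by 100 (no loss) and 100 × (1 − 0.56) = 44. The 44 is an assumption: the 56% is an overall figure taken from a study with at least ten years of follow-up, whereas the endpoint is at 24 months.

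**The plan's own figure.** The noncentrality is √10 × (82.16 − 65.40) / 16.76 = √10 × 1 = 3.162 on 9 degrees of freedom. The noncentral t gives power 80.31% two-sided at 5%, matching the stated 80.3%. One-sided 5% would give 89.75%.

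**False-pass rate at the boundary.** Draw n normal scores with mean 65.40 and SD 16.76, remove k subjects, and compute t = (mean − 65.40) / (SD / √(n − k)) from those left. Count a pass when t exceeds the upper 5% point on n − k − 1 degrees of freedom. There were 200,000 samples per setting.

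| Removal rule | n = 100 | n = 44 |
|---|---|---|
| None | 5.0% | 5.0% |
| 3 at random from all | 4.9% | 5.0% |
| 2 at random from the lowest quarter | 8.1% | 10.4% |
| 3 at random from the lowest quarter | 10.3% | 14.8% |
| Lowest 1 | 8.7% | 10.6% |
| Lowest 2 | 13.4% | 17.8% |
| Lowest 3 | 18.9% | 26.5% |

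For the lowest two or three, this multiplies the rate by 13.4/5.0 = 2.7 to 18.9/5.0 = 3.8 at n = 100, and by 17.8/5.0 = 3.6 to 26.5/5.0 = 5.3 at n = 44.

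**Sensitivity to the test and the score distribution.**
- Sign test, lowest two or three removed: 4.4% to 6.6% (n = 100) and 4.8% to 8.7% (n = 44).
- t-test with scores bounded at 0-100 (beta shape): 5.4% to 15-21% (n = 100) and 5.7% to 21-31% (n = 44).
- t-test at one-sided 2.5%, n = 44: 2.5% to 11-18%.

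**Sensitivity to the true mean** (t-test, n = 44, none removed against lowest three removed):
- 60: 0.01% against 0.3%.
- 62: 0.15% against 2.5%.
- 63: 0.5% against 6.0%.
- 82.16: passes essentially always, either way.

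So with 44 evaluable, even the worst case exceeds 5% only within about 2.4 to 3.4 points below the limit. At n = 100 the band is narrower: a true mean of 63 gives 1.1% after removing three.

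**The case against.** The strongest reply is that the documents already contain a safeguard. If anyone is excluded, both populations are to be fully analysed, so a PP pass that depended on exclusions would sit beside an ITT result in the final report. This stands in part. It exposes a discrepancy but does not settle it, since no population is named as decisive. ITT is absent from the annual report in which Protocol 11.5.1 and SAP 4.2 place the primary test. ITT is also itself restricted to eligible subjects, so it may not bring back everyone whom PP removes.

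A reader might infer that a filtered PP set will decide the claim. The documents do not say so: the sentence about analysing everybody per protocol expects no exclusions, in which case PP and ITT coincide. On the stated timing, a 24-month annual report also comes before the exclusion review.

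A reader might take 18-27% as the expected error rate. It is not. It requires that the excluded subjects be exactly the lowest scorers, that the true mean be 65.40, that the t-test apply, and that 44 be evaluable. No figure in the documents says how many deviations to expect or that they track low scores.

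A reader might cite the unblinded design as proof that the reviewer sees the scores. That statement concerns treatment; on the reviewer's access the documents are silent. The point rests on the review coming after completion with no provision to withhold scores.

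Finally, it would go too far to rest the claim on every subject whom PP removes. That would include subjects who never received the device.

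**Conclusion.** The point holds as a cheap improvement. The third PP criterion is open, worded by effect on outcome, and applied when scores are known. The ITT analysis is a real but incomplete safeguard, because it comes only in the final report and no deciding population is named.

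At a true mean of 65.40, with the t-test and two or three removals, the false-pass rate runs from 5% (removals unrelated to score), through 8-10% (n = 100) or 10-15% (n = 44) for partly selective removal, to 13-19% or 18-27% as the worst case. The sign test reaches about 7-9%. If the true mean is near the planning value of 82.16, the conclusion will not change.

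These figures assume normal scores with SD 16.76. The evaluable number, the count of removals and their link to score are assumptions, shown as ranges.

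**What to change.** In Protocol 11.2 and SAP 5.1:

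1. Replace the third criterion with a closed list of deviation types, fixed now.
2. State that the list is applied from the record of deviations alone, by someone without access to ASES scores or adverse-event outcomes, and signed off before the 24-month ASES data are opened. Access matters because SAP Table 6.5.2 puts ASES totals by visit into the annual reports.
3. Report the primary test with and without the subjects removed for deviations or eligibility, both at the same time and in the same report.
4. Name the deciding set: all subjects implanted with the ReUnion TSA System who have a 24-month ASES score. Subjects who never received the device stay out of it. This also fits Protocol 9.3, which keeps data up to withdrawal in the final analysis even after a selection-criteria violation.

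The cost is wording in two documents, and existing data-management staff can apply the list. The small downside is that an unforeseen type of deviation can no longer be excluded from the analysis that carries the claim. It can still be shown in a labelled sensitivity analysis.
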